5.1 Assignment of participant numbers

[figure not shown]
To manage study enrolment, each participant will be allocated a -character participant number comprised of a -digit study site number (01, 02, etc.) and a -digit number incremental per center representing the sequential order in which they are screened (01-001, 01-002, etc.). The -digit participant number will be used to identify the participant throughout the study.

6. Treatments

[figure not shown]
6.1 Details of study treatment and different phases

OPEN FACE MASK PHASE

NO MASK PHASE

6.2 Prior and concomitant medications

Before and during the period of radiotherapy administration there are no specific medications that are prohibited. We would ask the subject to mention if they took any anxiolytics the day of a session of radiotherapy because this could influence our results. This should be recorded in the CRF.

7. Study assessment

7.1 Time and events schedule

The procedures and assessment to be performed throughout the study are outlined in the time and events schedule.

Table 2. Time and events schedule for all participants

Procedure or assessment		Screening	During treatment
Informed consent procedure		x	
Eligibility criteria assessment		x	
ECOG Performance Status		x	
RTT appreciation 0-100			Q1wk
Dutch Claustrophobia questionnaire	Appendix 1	x	
Level of distress	Appendix 2		Q1wk
Treatment time			Every treatment session
In vivo dosimetry			Every first 3 sessions of every phase
Evaluation of the intrafractional motion			Every first 3 sessions of every phase

Abbreviations: Q1wk: weekly

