3.3 Secondary objective

Our secondary objective is:

- 3) to demonstrate that irradiation with open face masks and SS or no face masks and SS for patients with head and neck cancer reduces the patients' levels of distress when compared to irradiation with full thermoplastic masks.
- 4) to demonstrate that irradiation with open face masks and SS or no face masks and SS is feasible for the treating RTT's.

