3.4 Secondary endpoints

- 3) Level of distress of patients, determined by using the subjective units of distress scale (scale of 0-100).
- 4) Preferred delivery technique as evaluated by treating RTT's involved in this study.

Our hypothesis for this trial can be best described by the PICO (Patient Intervention Comparison Outcome):

- Patient: patients who are in need of primary treatment with radiotherapy for a histologically confirmed HNC
- Intervention: irradiation with SS and an open face mask; irradiation with SS but without a thermoplastic mask
- Comparison: standard of care treatment, irradiation with a full thermoplastic mask
- Outcome: accuracy of the irradiation (in-vivo dosimetry, intra-fractional motion during radiotherapy); duration of the irradiation in the different groups; results of claustrophobia questionnaires; results of RTT satisfaction questionnaires

4. Study population

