7.2 Study procedures

The study procedures are described in subsequent sections

Patient demographics and other screening characteristics

The data that will be collected at screening include:

- Demography (date of birth)
- ECOG performance status (Appendix 3)
- Patient questionnaire: the Dutch Claustrophobia questionnaire
- Use of anxiolytic medication

Accuracy assessments

- using PerFRACTION (in vivo dosimetry)
- using the intrafractional motion determined by the change in position between the CBCT pre and post treatment

Assessment of patients' distress level

-Weekly using the level of distress (see appendix)

Assessment of treatment time

-Will be done automatically using the radiotherapy delivery software

Assessment of RTT preference

- Using score of 0-100

8. Safety monitoring and reporting

ICH GCP and the EU Directive 2001/20/EC require that both investigators and sponsors follow specific procedures when notifying and reporting adverse events/reactions in clinical trials. These procedures are described in this section of the protocol.

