10.2 Statistical plan

A sample size of 24 patients was estimated to provide 95% power in order to rule out an excess of 2 mm in mean displacement, assuming a significance level of 0.05 (1-sided as testing for non-inferiority).

Mean displacements and standard deviations will be compared for the different delivery techniques for each patient. Using the method described by van Herk, population mean displacement (MD), systematic (R) and random (r) errors were estimated.

CBCT registration results will be analysed in 3-dimensions for each patient; population MD, R and r will be calculated. Paired t- tests will be used to compare the parameters listed above, and timing data (CT and treatment session times).

Patient comfort and acceptability questionnaires will be summarised as patient comfort scores ranging from 0 (most comfortable) to 100 (least comfortable).

RTT satisfaction questionnaires will be summarised as scores ranging from 0 (most satisfactory) to 100 (least satisfactory).

Statistical analyses will be performed using SPSS Statistics.

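### The objective of demonstrating feasibility for the RTTs is paired only with a preference endpoint, so the plan as written cannot support a feasibility conclusion

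*Combined protocol and SAP*

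**What the plan says.** The secondary objective for the RTTs (section 3.3, item 4; item 2 in the synopsis) is to demonstrate that "irradiation with open face masks and SS or no face masks and SS is feasible for the treating RTT's". The endpoint paired with it (section 3.4, item 4; item 2 in the synopsis) is "Preferred delivery technique as evaluated by treating RTT's involved in this study". No other endpoint is attached to this objective, and no feasibility criterion is given.

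The score behind the endpoint has three names:

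- Table 2 in section 7.1 lists "RTT appreciation 0-100", weekly, with no anchors and no appendix reference.
- Section 7.2 has "Assessment of RTT preference", described only as "Using score of 0-100".
- The outcome list in section 3.4 has "results of RTT satisfaction questionnaires". Section 10.2, repeated in the synopsis, says "RTT satisfaction questionnaires will be summarised as scores ranging from 0 (most satisfactory) to 100 (least satisfactory".

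The appendices cover the claustrophobia questionnaire, the distress scale and ECOG status. None is an RTT form.

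**The concern.** Feasibility is an absolute property: can the technique be carried out as planned, often enough, by the people who must do it? Preference is relative: which of three techniques do those people like best? An answer to the second question does not answer the first.

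The gap falls on what is newest in the trial. Section 1.1 gives the feasibility of maskless treatment as a reason for doing the study. If a maskless session could not be completed as scheduled, nothing in the endpoint for this objective would register it. At the end, the trial could report a ranking of techniques but could not support the claim that the objective sets out to demonstrate.

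The labelling is a lesser matter. People asked for an appreciation or preference score out of 100 will tend to give high numbers to what they like, whereas section 10.2 places the best score at 0. Without anchors at the point of scoring, different RTTs could use the scale in different directions.

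**Working it through.** The documents give no sample size, power or test for the RTT endpoint, so there is no planned figure to reproduce. The check sets objective against endpoint, counts the unused data, and sizes the labelling risk.

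**1. Objective against endpoint.** Take the two possible findings for the maskless technique.

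- RTTs rank it last. It may still have been delivered as scheduled every time, so feasibility is not refuted.
- RTTs rank it first. All three techniques may have been hard to deliver, so feasibility is not shown.

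Neither result settles the objective. The mean 0-100 score could be read on its own as a measure of acceptability, but section 10.2 sets no value that would count as feasible.

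**2. Data that bear on feasibility.** Inputs from sections 2 and 5: 24 patients, 35 fractions each, technique changed every 5 fractions, three schedules of 8 patients.

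- Planned fractions: 24 x 35 = 840.
- In each schedule the starting technique has 3 blocks (15 fractions) and the other two have 2 blocks each (10 fractions).
- Each technique starts one schedule, so it has 8 x 15 + 16 x 10 = 120 + 160 = 280 planned fractions.

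These counts assume no withdrawals. Section 4.3 says that patients who withdraw are not replaced, so 280 is a maximum.

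**3. How much information 280 fractions carry.** They come from 24 patients, on average 280 / 24 = 11.7 per patient. If fractions within a patient were independent, the information would be that of 280 observations. If all of a patient's fractions went the same way, it would be that of about 24 (patients weighted equally). A simple binomial interval could then be too narrow by a factor of up to about √(280 / 24) = 3.4. The true position between these limits is not known from the documents.

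**4. Mixed scoring directions.** Let D be the true difference between two techniques and p the share of ratings given in the opposite direction. The reported difference is (1 − p)D − pD = (1 − 2p)D. For an assumed D of 20 points:

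| p (assumed) | reported difference |
|---|---|
| 0 | 20 |
| 0.10 | 16 |
| 0.25 | 10 |
| 0.50 | 0 |
| 0.75 | −10 |
| 1 | −20 |

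A uniform and known reversal is repaired by taking 100 minus the score. A mixture cannot be repaired unless each rating's direction was recorded.

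**The case against.** The sponsor can fairly say that feasibility for the RTTs means workability as staff judge it, and that a weekly 0-100 score is an absolute rating, not merely a rank. This stands in part: the score is useful evidence of acceptability. It does not close the gap, because the endpoint is worded as the preferred technique and no score is said to be adequate.

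The sponsor can also point out that the trial records relevant facts elsewhere. Treatment time is captured at every session (7.1), protocol deviations are documented (10.3), and changes in treatment go into the eCRF (11.6). So it would be wrong to infer that failed deliveries leave no record at all. What is missing is the link: none of these is tied to the feasibility objective, and treatment time is listed under the primary endpoint. The figures in section 6.1 could not be read. They may describe the phases further, but the endpoint itself is defined in section 3.4.

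On the score, a reader might infer that the RTT ranking will come out reversed. The documents do not support that. The only written direction is 0 as best, given identically in the synopsis and section 10.2. The labels in sections 7.1 and 7.2 carry no anchors, so high-is-good is a natural reading of a word and not a stated rule. The RTT form is not in the documents and may print the right anchors. Low-is-good also matches the comfort and distress scales, so there is no case for turning the RTT scale round.

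Finally, this is a secondary endpoint that is summarised without a test. It affects neither the sample size nor the accuracy comparison.

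**Conclusion.** The mismatch between objective and endpoint holds. Followed as written, the plan can report which technique RTTs prefer but cannot support a conclusion that open-mask or maskless treatment is feasible for them. Delivery as scheduled, over up to 280 planned fractions per technique, plays no part in the endpoint. That count rests on 24 patients completing all 35 fractions.

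The labelling point holds only as a risk. One score has three names, and only one of them carries anchors, which run against the ordinary sense of the other two. The size of any resulting dilution depends on a share p that the documents do not give. An actual reversal is not shown.

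The sponsor should act on this, but it is limited to a secondary, descriptive part of the trial.

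**What to change.** For the RTT feasibility objective, add as its endpoint, for each technique, the proportion of scheduled fractions delivered in full with the assigned technique. Specify:

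- the denominator, including how fractions after a withdrawal are counted;
- a confidence interval that allows for repeated fractions within patients, for example a patient-level bootstrap or GEE;
- a criterion fixed before data collection, if the word *demonstrate* is to stay. Without one, the proportion is only descriptive and has the same weakness as the present endpoint.

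Keep the RTT score as supportive evidence of acceptability. If the sponsor does not want a delivery endpoint, the minimum change is to restate the objective as RTT preference in section 3.3 and the synopsis.

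For the score, use one name throughout. Print the existing section 10.2 anchors on an appended RTT form beside the technique being rated, and repeat them in sections 7.1 and 7.2. This must be done before scoring starts, since mixed directions cannot be untangled later.

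The cost is protocol wording, one short form and, if the delivered technique is not already recorded, one CRF field per fraction. The documents do not say whether it is recorded: section 7.2 mentions the delivery software only for treatment time.

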7.2 Study procedures

The study procedures are described in subsequent sections

Patient demographics and other screening characteristics

The data that will be collected at screening include:

- Demography (date of birth)
- ECOG performance status (Appendix 3)
- Patient questionnaire: the Dutch Claustrophobia questionnaire
- Use of anxiolytic medication

Accuracy assessments

- using PerFRACTION (in vivo dosimetry)
- using the intrafractional motion determined by the change in position between the CBCT pre and post treatment

Assessment of patients' distress level

-Weekly using the level of distress (see appendix)

Assessment of treatment time

-Will be done automatically using the radiotherapy delivery software

Assessment of RTT preference

- Using score of 0-100

8. Safety monitoring and reporting

ICH GCP and the EU Directive 2001/20/EC require that both investigators and sponsors follow specific procedures when notifying and reporting adverse events/reactions in clinical trials. These procedures are described in this section of the protocol.

8.1 Adverse event definitions and classifications

Definitions in Law of May 7, 2004 concerning experiments on the human person:

Adverse event (AE):

An adverse event is any untoward medical occurrence in a patient or clinical investigation subject which does not necessarily have a causal relationship with treatment.

Serious adverse event (SAE):

An SAE is any untoward medical occurrence that:

- results in death
- is life-threatening
- requires inpatient hospitalisation or prolongation of existing hospitalisation
- results in persistent or significant disability or incapacity
- is a congenital anomaly or birth defect
- is medically important (medical and scientific judgement should be exercised in deciding whether expedited reporting is appropriate in other situations, such as important medical events that may not be immediately life-threatening or result in death or hospitalisation but may jeopardize the patient or may require intervention to prevent one of the other outcomes listed in the definition above).

Relationship of AEs to the intervention under investigation is assessed using the following scale: related (that is, it resulted from any of the research procedures)/unrelated.

Unexpected AE are events that are not listed in the protocol as an expected occurrence.

Severity criteria: the NCI-CTCAE (version 5.0 or later) will be used to grade the severity of adverse events.

The assignment of the relationship/severity should be made by the investigator responsible for the care of the participant. The sponsor of the study has delegated the assessment of expectedness to the study responsible physician or his delegate. The expectedness assessment will be performed and compared to known complications for this type of radiotherapy.

8.2 Reporting procedures

Period of observation

Table 2: Reporting period for AEs and SAEs

Period	AEs (non-serious)	SAEs
From: Main ICF signature To: Day 1 of the intervention under investigation	Only if related to trial participation	All (regardless of relationship)
From: Day 1 of the intervention under investigation To: 30 days after last treatment	All (regardless of relationship)	All (regardless of relationship)

Reporting

All AEs must be recorded using medical terminology in the source document and the eCRF. Whenever possible, diagnoses should be given when signs and symptoms are due to a common etiology (e.g., cough, runny nose, sneezing, sore throat, and head congestion should be reported as "upper respiratory infection"). Investigators must record in the eCRF their opinion concerning the relationship of the adverse event to treatment.

The investigator shall report all serious adverse events immediately (<24h), after first knowledge, to the sponsor. Information regarding SAEs will be transmitted to the sponsor using the SAE form, which must be completed and signed by a physician from the study site and transmitted to the sponsor ([contact]) within 24 hours.

All SAEs that have not resolved by the end of the study or that have not resolved upon discontinuation of the subject's participation in the study, must be followed until any of the following occurs:

- the event resolves
- the event stabilizes
- the event returns to baseline, if a baseline value/status is available
- the event can be attributed to agents other than the treatment or to factors unrelated to study conduct
- it becomes unlikely that any additional information can be obtained (subject or health care practitioner refusal to provide additional information, lost to follow-up after demonstration of due diligence with follow-up efforts)

The immediate and follow-up SAE reports shall identify subjects by patient specific study numbers.

The following situations do not need to be reported as SAEs:

- Elective hospitalization for pre-existing conditions that have not been exacerbated by the treatment;
- A hospitalization which was planned before the patient consented for study participation and where admission did not take longer than anticipated;
- A hospitalization planned for protocol-related treatment or protocol-related procedure as per institutional standard timelines;
- Social and/or convenience admission to a hospital;
- Medical or surgical procedure, e.g., endoscopy, appendectomy; unless the condition that leads to the procedure is an (S)AE.

- Situations where an untoward medical occurrence did not occur (palliative care, rehabilitation, overdose without occurrence of an AE);
- Anticipated day-to-day fluctuations of pre-existing disease(s) or condition(s) present or detected at the start of the study that do not worsen.

For reported death of a subject, the investigator shall supply the sponsor and the accredited ethics committee with any additional information requested.

The sponsor shall keep detailed records of all adverse events which are reported to him by the investigators. These records shall be submitted to the minister if the experiment is being conducted in Belgium, if he so requests.

Notification of serious adverse events

The sponsor shall ensure that all relevant information about related unexpected serious adverse events that are fatal or life-threatening is recorded and reported as soon as possible to the competent ethics committee, and in any case no later than seven days after knowledge by the sponsor of such a case, and that relevant follow-up information is subsequently communicated within an additional eight days.

All other suspected unexpected serious adverse reactions shall be reported to the ethics committee concerned as soon as possible but within a maximum of fifteen days of first knowledge by the sponsor. The sponsor shall also inform the other investigators.

Once a year throughout the experiment, the sponsor shall provide the ethics committee with an annual safety report, listing all suspected serious adverse reactions which have occurred over this period and a report of the subjects' safety (development safety update report). Regarding those adverse events and serious adverse reactions the Study responsible physician will take all reasonable measures, in consultation with Sponsor, to protect subjects at risk following the occurrence of such events.

9. Data management

9.1 Data collection

Data required by the protocol will be entered in an Excel based database. The PI and [name], [name] and [name] will have access to this database.

These patients will be numbered and anonymised according to the moment of inclusion. Database will be excel-based and Access-based.

10. Statistical considerations

10.1 Justification of sample size

A sample size of 24 patients was estimated to provide 95% power in order to rule out an excess of 2 mm in mean displacement, assuming a significance level of 0.05 (1-sided as testing for non-inferiority).

10.2 Statistical plan

A sample size of 24 patients was estimated to provide 95% power in order to rule out an excess of 2 mm in mean displacement, assuming a significance level of 0.05 (1-sided as testing for non-inferiority).

Mean displacements and standard deviations will be compared for the different delivery techniques for each patient. Using the method described by van Herk, population mean displacement (MD), systematic (R) and random (r) errors were estimated.

CBCT registration results will be analysed in 3-dimensions for each patient; population MD, R and r will be calculated. Paired t- tests will be used to compare the parameters listed above, and timing data (CT and treatment session times).

Patient comfort and acceptability questionnaires will be summarised as patient comfort scores ranging from 0 (most comfortable) to 100 (least comfortable).

RTT satisfaction questionnaires will be summarised as scores ranging from 0 (most satisfactory) to 100 (least satisfactory).

Statistical analyses will be performed using SPSS Statistics.

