Participant selection criteria:	
Each potential subject must satisfy all of the following criteria to be enrolled in the study.
 
 - Patients \geq 18 years old - Histologically confirmed head and neck cancer. - Patients treated with RT as primary treatment. - An Eastern Cooperative Oncology Group (ECOG) Performance Status grade of 0-1. - Each subject must sign an informed consent form (ICF) indicating that he understands the purpose of and procedures required for the study and is willing to participate in the study. - Patients must be willing to comply with treatment plan and other study procedures. 
Each potential subject must NOT have any of the following criteria to be enrolled in the study.
 
 - Patients with significantly altered mental status or with psychological, familial, sociological or geographical condition potentially hampering compliance with the study. - Individual deprived of liberty or placed under guardianship. - Patients who cannot stay still during fraction because of a disorder (e.g. Parkinson's disease)
Treatment:	
The treatment of every patient will be divided into different phases:
 
 -patients will be irradiated with an open face mask and SS -patients will be irradiated with SS without a mask -patients will be irradiated with a full thermoplastic mask 
The delivery technique will change for every patient each 5 fractions. The first 8 patients included in the study will have the following schedule: full mask-open mask-no mask-full mask-...
 
The 9th till 16th patient included in the study will have the following schedule: open mask-no mask-full mask-open mask-...
 
The 17th till 24th patient included in the study will have the following schedule: no mask-full mask-open mask-no mask-...

Duration of study:	12 months
Accuracy:	
 - In-vivo dosimetry using PerFRACTION - Evaluation of intrafractional motion by comparing a CBCT before and at the end of treatment
Statistical methods:	A sample size of 24 patients is estimated to provide 95% power in order to rule out an mean displacement in excess of 2 mm, assuming a significance level of 0.05 (1-sided as testing for non-inferiority).

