1.1 Background & rationale

Head and neck cancer (HNC) is a broad term that encompasses a large number of tumour entities originating from different subsites, such as the nasal cavity, nasopharynx, oral cavity, oropharynx, larynx, hypopharynx and salivary glands.

In Belgium, in the year 2016 (latest data Belgian Cancer Registry), more than 2500 patients were diagnosed with head and neck cancer. (1) In the United States, for the year 2014, there was an estimate of 55.070 new cases of HNC (2). Approximately 60% to 80% of HNC patients present with loco-regionally advanced disease at time of diagnosis. The main treatment options for loco-regionally advanced HNC are (chemo-) radiotherapy (RT) and surgery (often followed by RT). During each RT course, patients are immobilised using a thermoplastic mask (**Figure 1 a.**) to limit the possibility to move during the treatment. Furthermore, this mask enables correct positioning before the start of each RT session.

[figure not shown]

Figure 1. Full thermoplastic mask (a.) and open thermoplastic mask (b.).

The use of these masks results in the following disadvantages:

- They can cause claustrophobia and anxiety. (3, 4, 6)
- Intrafractional surface monitoring is not possible with closed masks. (3)
- Full-face masks can be very uncomfortable and cause pain by pressure. (5, 6, 7)
- The masks don't adapt to weight loss or edema that can occur during radiotherapy.

Lately, to reduce these side effects, there is an interest in using open face masks (**Figure 1 b.**) in combination with surface scanning (SS). SS is a system which tracks a patient's position before and during RT, to aid in setup and treatment accuracy. Using 3D stereo camera units, the SS tracks the skin surface, and compares it to the ideal position. (4) The combination of an SS and an open face mask therefore enables us to monitor intrafractional movement. (8) This system can then automatically signal the treatment delivery system to pause radiation if the patient moves out of the desired position.

The use of SS together with open face masks for HNC has been studied. An overview of the relevant literature review can be found in **Table 1**.

Article	Number of participants	Hypothesis	Conclusion

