3.1 Primary objective

We would like to investigate whether irradiation with open face masks and SS, and without masks and SS, for patients with head and neck cancer is at least as good as irradiation with a full thermoplastic mask in terms of set-up and treatment accuracy.

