3.2 Primary endpoint

- 1) Set-up and treatment accuracy, determined by in-vivo dosimetry using PerFRACTION, and by the evaluation of intrafractional motion by comparing a CBCT before and at the end of treatment in patients receiving RT with an open mask, without a mask and using a closed thermoplastic mask.
- 2) Average treatment time for the different deliveries (full mask, open mask, without a mask)

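### The 2 mm non-inferiority margin is set on a mean displacement that is not defined as signed, absolute or 3D length, and these readings can give different verdicts

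*Combined protocol and SAP*

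**What the plan says.** The primary objective (3.1) is to show that treatment with an open mask or no mask, with surface scanning, "is at least as good as irradiation with a full thermoplastic mask in terms of set-up and treatment accuracy". One part of the primary endpoint (3.2) is the "evaluation of intrafractional motion by comparing a CBCT before and at the end of treatment".

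Sections 10.1 and 10.2 justify 24 patients as giving 95% power, at one-sided 0.05, to "rule out an excess of 2 mm in mean displacement". The synopsis instead says "rule out an mean displacement in excess of 2 mm". Read literally, that is a ceiling on displacement itself, but it is probably loose wording for the same comparison.

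On analysis, section 10.2 says: "Mean displacements and standard deviations will be compared for the different delivery techniques for each patient". It then says: "CBCT registration results will be analysed in 3-dimensions for each patient; population MD, R and r will be calculated". It adds that paired t-"tests will be used to compare the parameters listed above". Section 7.2 describes the raw measure only as the change in position between the two CBCTs. No section gives a sign convention, a formula, an axis rule, an SD or an assumed true difference. The reference list does not contain the source of the method named for MD, R and r.

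**The concern.** A pre-to-post CBCT shift is a three-component vector. It can be averaged with sign on each axis, as an absolute value on each axis, or as a length. These quantities behave differently when immobilisation is lost. Looser immobilisation would be expected to produce larger shifts in varying directions. A signed mean averages those away: +4 mm and -4 mm give 0. A magnitude does not.

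The only population summary named is MD, listed beside systematic and random errors. If MD is a signed mean, the single margin sits on the quantity least able to detect extra motion. If the choice stays open, it could be made after the data are seen. Per-patient SDs and in-vivo dosimetry are also assessed, but neither has a margin, and no rule says how they count if the 2 mm test is met and they are worse.

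A second, smaller problem is that the paired t-tests are to cover all the listed parameters, and some of these have no per-patient value to pair.

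**Working it through.** **Inputs from the documents.** N = 24, margin 2 mm, one-sided 0.05 and 95% power (10.1, 10.2). There are seven phases of five fractions (section 2), and motion is measured in the first three sessions of each phase (7.1). The numbers of measured sessions, full mask / no mask, are therefore 9/6, 6/6 and 6/9 in the three groups of eight. All SDs below are assumptions.

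**1. The plan's own figure.** For a paired test at zero true difference, n = (SD × (1.645 + 1.645) / 2)². Setting n = 24 gives SD = 2 × √24 / 3.290 = 2.98 mm, or 2.89 mm with the noncentral t on 23 df. The plan states no SD, so 24 cannot be reproduced. About 2.9 mm is only what it implies.

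**2. True excess under each reading.** Take zero-mean normal motion, equal on the three axes, with per-axis SD σ = √(random² + systematic²). Let G be the no-mask σ minus the full-mask σ.
- Signed mean: excess 0, whatever G is.
- Absolute per-axis mean: 0.798 × G, above 2 mm when G exceeds 2 / 0.798 = 2.51 mm.
- 3D length: 1.596 × G, above 2 mm when G exceeds 2 / 1.596 = 1.25 mm.

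Since 1.596 / 0.798 = 2, a margin of 2 mm on 3D length is as strict as 1 mm on an absolute per-axis mean.

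Example: random 1 vs 3 and systematic 0.5 vs 1.5 mm give σ = √1.25 = 1.118 and √11.25 = 3.354, so G = 2.236. The excesses are 0, 0.798 × 2.236 = 1.8 mm and 1.596 × 2.236 = 3.6 mm.

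**3. Simulated verdicts.** There were 4,000 trials per row. A reading passes if the one-sided 95% t bound on the within-patient difference is inside 2 mm. Signed requires all three axes in both directions; absolute requires all three axes.

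| Per-axis SDs, full vs no mask (mm) | True excess, signed / absolute / 3D (mm) | Pass rate, signed / absolute / 3D |
|---|---|---|
| random 1 vs 3, no systematic | 0 / 1.6 / 3.2 | 100% / 56% / 0% |
| random 1 vs 3, systematic 0.5 vs 1.5 | 0 / 1.8 / 3.6 | 99% / 4% / 0% |
| both 1 vs 2 | 0 / 1.1 / 2.3 | 95% / 88% / 0.5% |
| random 0.5 vs 1, systematic 0.25 vs 0.5 | 0 / 0.4 / 0.9 | 100% / 100% / 100% |

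**4. The axis rule.** With two identical techniques (both SDs 2 mm), signed passes in 81% of trials if only the upper limit must hold on all axes, and in 65% if both directions must. 3D length passes in 100%. The open definition can therefore also fail an equivalent technique.

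**5. Effect of a beam pause.** Holding no-mask shifts at a 3 mm cap, with the SDs of the second row, gives 100% on all three readings (3D excess 1.1 mm). For both SDs 1 vs 2, a 4 mm cap also gives essentially 100% on all three.

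**6. The paired tests.** Per-patient means and SDs give 24 pairs per comparison. Population MD, R and r are one number per technique and axis, so there is nothing to pair across patients.

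**The case against.** **The signed reading is not established.** The wording of a one-sided excess fits a magnitude at least as well, because under a signed mean a large negative shift would pass an upper-limit test. This stands. Signed is one possible reading, suggested by MD sitting beside R and r. A reader might infer that the plan adopts it; the documents do not say so.

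**Part of the contrast is a change of scale.** In the three divergent rows the true absolute per-axis excess is 1.6, 1.8 and 1.1 mm, all inside 2 mm. The absolute failures are lack of power, and a signed pass is wrong only against a 3D yardstick of 2 mm. This also stands, and it is why 2 mm must be confirmed for whichever variable is chosen.

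**Surface scanning can limit motion.** Section 1.1 says the system can "automatically signal the treatment delivery system to pause radiation if the patient moves out of the desired position". Little of section 6.1 survives in the text available, so a tolerance may be stated there. The uncapped scenarios may not describe this trial. A reader might look for one shift size at which the readings part, but there is none. With shifts held at 5 mm, the second row's SDs give a 3D excess of 2.5 mm. With both SDs 1 vs 2, the excess is still 1.98 mm at 6 mm.

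**Other results would reveal lost immobilisation.** A paired test on per-patient log SDs detects the difference in 100% of simulated trials in the three divergent rows. The plan would therefore show a conflict, but it has no rule for settling it.

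**The t-test sentence can be read as per-patient values only.** That is a workable reading, but the list to which the sentence points includes the population quantities.

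**Conclusion.** The concern holds in this form. The only non-inferiority margin rests on an undefined quantity, and defensible definitions can disagree. At random SD 1 vs 3 and systematic SD 0.5 vs 1.5 mm, the pass rates run from about 99% (signed) to 4% (absolute) to 0% (3D length). With small motion or tight capping all readings agree. The size rests on assumed SDs, zero-mean normal motion, equal axes and no cap, and how likely a reversed verdict is cannot be judged from the documents.

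A reader might conclude that the test cannot be run at all. That is too strong: several versions can be run, and the defect is that the plan does not say which one decides. Nor do the documents show that a maskless technique would wrongly pass. They show only that the plan leaves room for it.

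The point about pairing population MD, R and r holds without any assumption about SDs.

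**What to change.** Before analysis:
- Define the primary motion variable as each patient's mean 3D vector length of the pre-to-post CBCT shift under each technique, and apply the margin to the within-patient difference from full mask.
- Confirm that 2 mm is meant for that variable, and state the SD behind N = 24 and 95% power.
- Align the synopsis with 10.1 and 10.2.
- Say how per-patient SDs and dosimetry count if the margin is met but they are worse.
- Report signed MD, R and r per axis as supporting results, and limit paired t-tests to per-patient means and SDs.

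Absolute per-axis means are not an equal substitute at 2 mm: they pass 88% of trials in the third row, where the 3D excess is 2.3 mm.

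The cost is wording in the synopsis, 10.1 and 10.2, and a recheck of the margin and power. No new data are needed. Power should not suffer if the techniques are equal: with random/systematic SDs from 1/0.5 to 3/3 mm, the simulated paired SD of 3D length is 0.4 to 2.4 mm and power is 99% to 100%. There are two downsides. 3D length loses direction, which is why the signed results stay in the report. Its simulated false-pass rate at a true excess of exactly 2 mm is 5.4% to 6.1%, slightly above the nominal 5%.
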